The power estimate is based on assessment of the primary outcome, treatment step, at 6 months. In the ICAS trial, the ECS resulted in a reduction of 0.8 symptom days/2 weeks within two months of randomization.⁽¹³⁾ The authors of the paper make the point that this effect size is similar to that seen with controller medications. In PREACH, the SHS intervention trial, there was an increase of 1.9 symptom-free days/2 weeks at six months in the group receiving air purifiers compared to the control group. This effect, which was observed with air purifiers alone and no other environmental intervention, is also similar in magnitude to low dose, inhaled corticosteroids, which resulted in an increase of 2 symptom-free days/2 weeks compared to placebo among children with persistent asthma (CAMP).⁽⁹⁾ With a multi-faceted intervention as proposed for this study, we expect a significantly larger effect size than observed with air purifier deployment alone. In terms of treatment step, low dose ICS is one “step-up” from no controller medication, which reflects the difference in controller medication requirement that our proposed study is powered to detect. Further, a 1 step reduction in controller medication requirement would also be the point at which an ECS would likely be cost effective. For example, in the ICAS trial,⁽¹³⁾ the intervention, which was effective for two years, cost approximately \$1500, similar to the cost of a one year supply of low dose ICS. There will be 7 possible treatment steps (Table 6) and, based on the distribution of participants across treatment steps in other studies, we will assume a mean treatment step of 4.0 at baseline among participants in both groups and have estimated the power to detect a difference of 1 treatment step between the two groups, with a standard deviation between 1.5 and 2. With a sample size of 200, and assuming alpha=0.05, we will have a power of 0.94 to detect a difference of this magnitude. With a drop-out rate of ~12%, there will be a power of 0.90. (Table 6)

Treatment step difference	SD	Power for n=200	Power for n=175
0.75	1.5	0.94	0.90
	2.0	0.75	0.69
1.00	2.0	0.94	0.90
	2.5	0.80	0.74

Analysis Plan

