The primary outcome will be the treatment step that is assigned at the final clinic visit at six months. The six month time point has been chosen because successful ECS trials have observed an effect by six months, but an effect may not be observed before this time because it takes several months for indoor allergen levels to fall after implementing an environmental intervention. The secondary outcome will be total daily ICS dose assigned at this same visit, expressed in milligrams. The primary analysis dataset will be an intent-to-treat (ITT) dataset and will include participants with six month outcome data collected, regardless of whether they completed all of the ECS activities. A per-protocol analysis will also be performed and will be performed on the dataset of participants with six month

outcome data who completed at least one intervention visit (one IPM visit or for the Medication Group, receipt of ECS educational materials). Exploratory data analysis for both Aims 1 and 2 will include compilation of descriptive statistics to detect any outliers or discrepancies in data and to compare baseline characteristics and demographics between ECS+Medication and Medication Groups. Continuous variables will be summarized using means, medians, standard deviations, ranges, and interquartile ranges. Continuous variables will be analyzed using non-parametric approaches or will be transformed to meet assumptions of normality required for parametric statistics. Categorical variables will be tabulated. The percent of participants who complete the study, losses to follow-up, missed visits, and reasons for discontinuation will be presented.

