The primary outcome will be the participant's assigned treatment step at the six month clinic visit (as described above). Secondary outcomes include: (1) daily inhaled corticosteroid dose, (2) allergic inflammation markers (allergen-specific IgE, FENO₂), (3) measures of asthma control (days of short-acting beta agonist use, days of slowed activity due to asthma, days of exercise-induced symptoms, days of cough without an upper respiratory infection, nights of waking due to asthma symptoms), and (4) measures of exacerbations (oral corticosteroid bursts, hospitalizations, emergency department visits, and unscheduled physician visits). Other secondary outcomes include FEV₁/FVC, % change in FEV₁ after albuterol, and asthma severity, as measured by the CASI.⁽²⁹⁾ We will subtract baseline levels of the treatment step from the step assigned at the 6 month CV to assess the within-person change in treatment step over time. Differences over time in the intervention group will be compared to those in the control group using a generalized linear modeling approach and a significance cutoff of 0.05. Assessment of significance adjusting for multiple comparisons will be done using the method of Benjamini and Hochberg.⁽³⁷⁾ Regression models will be used to adjust for potential confounders and to test for interactions with potential effect modifiers. A similar analytic approach will be used for other clinical and inflammation outcomes, with appropriate statistical tests and models for the different types of outcome variable data, such a Chi-Square test and logistic regression for dichotomous outcomes.

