Potential confounders will be explored by examining any differences between the intervention and control groups and also assessing the association between the potential confounders at baseline and at the final study visit. In addition, potential confounders will be included in the models to determine the impact the variables have on the relationship between group assignment and the outcome. Some specific confounders that will be carefully examined include baseline allergen and pollutant levels, treatment step at baseline, and season. Potential effect modifiers, such as baseline pollutant and allergen levels, baseline asthma severity, baseline asthma control, baseline lung function, and number of positive skin tests, will also be examined by stratifying analyses and creating an interaction term to include in the final models. Analyses will be stratified by these potential response predictors and interaction terms will be included in models to determine if any of these factors predict responsiveness to the intervention.

To measure the change in home airborne particulate matter (PM_{2.5} and PM_{2.5-10}) and indoor allergen concentrations (cat, dog, mouse, cockroach, and dust mite) among study participants. Distributional properties of baseline levels of pollutants (PM_{2.5} and PM_{2.5-10}) and allergens will be assessed using histograms and boxplots and any necessary transformations to these variables will be conducted to obtain approximately Normal distributions. We will subtract baseline levels of these exposures from levels recorded 6 months post-randomization to assess the within-person change in exposure over time. Differences over time in the intervention group will be compared to those in the control group via standard *t*-tests using a significance cutoff of 0.05. Assessment of significance adjusting for multiple comparisons will be done using the method of Benjamini and Hochberg.

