To evaluate the role of bacterial communities and *S. aureus* colonization on asthma morbidity, we will perform exploratory data analysis to identify outliers and missing data, and to generate descriptive summaries of multiple outcome variables related to asthma morbidity. The primary predictive variable will be *S. aureus* colonization. We will test *S. aureus* association with asthma outcomes over multiple visits using random effects models. In order to adjust for potential confounders, such as child demographic characteristics, *etc.*, we will construct multivariate random effects models that account for repeated assessment of the outcomes and time-varying covariates. For bacterial community analysis, we will compare taxonomical relative abundances using the Wilcoxon rank-sum test. Accounting for clustering within home and host, we will identify the influence of demographic and other factors on

microbial composition by calculating the weighted and unweighted UniFrac and the non-parametric ANOSIM (ANalysis of SIMilarities) test.

d. Early stopping rules.

The protocol may be halted by the DSMB, IRB or Sponsor upon review of SAEs.

7. Risks

a. Medical risks, listing all procedures, their major and minor risks and expected frequency.

Questionnaires

The risk of the questionnaire is breach of confidentiality.

Blood draw

The risk of blood drawing is discomfort, bruising, lightheadedness, and rarely infection.

Lung function and exhaled nitric oxide testing

The risk of lung function and eNO testing is the discomfort of exhaling forcefully, light-headedness and occasional minor chest soreness.

Home visits

The risk of the home visit for collection of environmental data is breach of confidentiality.

Skin testing

The risk of skin testing is primarily the discomfort from any positive skin tests, which would result in wheal and flare responses and pruritus. Approximately 2-3 in 10,000 skin prick tests results in allergic symptoms away from the site of the skin testing, such as sneezing, rhinorrhea, or rash.^(38, 39) Very rarely, an individual who experiences this type of reaction may develop life-threatening symptoms such as persistent coughing or wheezing. A study published in 1987 reported six fatalities from skin testing since 1945.⁽³⁹⁾ From 1985-1989 there were no fatalities from skin testing reported,⁽⁴⁰⁾ and one fatality was reported from 1990-2001.⁽⁴¹⁾

Buccal Cell Collection

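### The set labelled ITT is an available-case set: no planned efficacy analysis covers every randomised child, and treatment step has no missing-data method despite about 12% expected loss

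*Combined protocol and SAP*

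**What the plan says.** Section 6.c, Analysis Plan, defines two analysis sets.

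- Primary: "The primary analysis dataset will be an intent-to-treat (ITT) dataset and will include participants with six month outcome data collected". The sentence goes on to keep children whether or not they completed the ECS activities.
- Per-protocol: "A per-protocol analysis will also be performed and will be performed on the dataset of participants with six month" outcome data, with at least one intervention visit also required (for the Medication Group, receipt of the educational materials). It is nested in the first set. No third set is defined.

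The primary comparison needs the final step: "We will subtract baseline levels of the treatment step from the step assigned at the 6 month CV". The change is compared between arms by a generalized linear model. Baseline step appears among the covariates to be explored: "Some specific confounders that will be carefully examined include baseline allergen and pollutant levels, treatment step at baseline, and season".

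On loss, the Power Estimate says "With a drop-out rate of ~12%, there will be a power of 0.90", and the Analysis Plan says "The percent of participants who complete the study, losses to follow-up, missed visits, and reasons for discontinuation will be presented". For treatment step, section 6.c names no imputation, weighting, likelihood-based method, missingness assumption or sensitivity analysis.

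Three other places bear on who is missing. Under Study Procedures, the paragraph on run-in and follow-up visits applies the treatment algorithm at clinic visits every two months, so a step is assigned at CV2, CV3 and CV4. Item f stops further study intervention after certain asthma hospitalisations, without saying whether CV4 still takes place. Item g replaces children who leave before CV2, and provides for a final telephone interview and referral back to the usual provider.

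**The concern.** An analysis of all randomised children protects the comparison that randomisation created. Here both sets are conditioned on something observed after randomisation, namely attendance at six months. The second set drops the same absent children as the first, so it cannot show whether their absence matters. The tabulation of losses may reveal an imbalance, but not its effect on the arm contrast.

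Loss could be related to outcome. Families know their arm (Study Procedures, item c), and the course of the asthma may affect whether they stay. Two counting rules are also open. The plan does not say whether a replaced child remains in the analysis, and the six-month rule would leave that child out. Nor does it say whether a child discontinued under item f is still assessed at CV4. If replaced children are counted as randomised, the number randomised can exceed 200, and the documents do not say which denominator the 12% uses.

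What is at stake is the primary contrast when the result lies near the significance threshold. The stated rule also sets aside information already in hand, because a child lost between CV2 and CV4 has one or two post-randomisation steps on record.

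**Working it through.** **1. The plan's own figure.** Inputs from the Power Estimate: 200 children 1:1, alpha 0.05 (taken as two-sided), difference 1 step, SD 2.0. A two-sample t-test gives power 0.940 at n=200 and 0.908 at n=175, against the stated 0.94 and 0.90. The power figures are therefore sound for an available-case analysis of about 175 children. Expected loss is 0.12 × 200 = 24, leaving 176, or 88 per arm.

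**2. Bias formula.** In each arm let m be the fraction missing and g the mean change in step of missing minus observed children. The full-arm mean is the observed mean + m·g. The observed ECS-minus-Medication contrast therefore differs from the full contrast by

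bias = m(Med)·g(Med) − m(ECS)·g(ECS).

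It is zero if both gaps are zero, however unbalanced the loss, and zero if loss and gap are both equal across arms.

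**3. Illustration.** The documents give neither loss by arm nor any gap, so the splits and gaps below are assumptions around the stated 12%. There is no baseline adjustment. SD 2.0 is taken as the SD of the analysed quantity, with 100 randomised per arm. Type I error is the two-sided t-test rejection rate with noncentrality bias/SE, where SE = 2.0·√(1/n1 + 1/n2).

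| Loss in the two arms | Gap in the two arms (steps) | Size of bias (steps) | Type I error |
|---|---|---|---|
| 12% / 12% | equal | 0 | 5.0% |
| 10% / 14% | 1 / 1 | 0.04 | 5.2% |
| 10% / 14% | 2 / 2 | 0.08 | 5.8% |
| 8% / 16% | 2 / 2 | 0.16 | 8.2% |
| 12% / 12% | 1 / 0 | 0.12 | 6.8% |
| 6% / 18% | 2 / 2 | 0.24 | 12.4% |
| 12% / 12% | 2 / 0 | 0.24 | 12.4% |

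Worked line: for 6% / 18% with a 2-step gap, bias = 0.18 × 2 − 0.06 × 2 = 0.24; SE = 2.0·√(1/94 + 1/82) = 0.302; noncentrality = 0.79; rejection rate 12.4%. Exchanging the arms reverses the sign. If the bias instead masks a true 1-step effect, the remaining contrast is 0.96 (bias 0.04) to 0.76 (bias 0.24), and power is 0.89 to 0.71.

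**4. Where a verdict could change.** With 88 per arm, SE = 2.0·√(2/88) = 0.3015, and the smallest significant difference is 1.974 × 0.3015 = 0.595. At the extreme of 0.24:

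- Bias away from the null: observed differences of 0.595 to 0.835 could lose significance. By normal approximation, an estimate falls there with probability 31% if the true difference is 0.75, and 20% if it is 1.0.
- Bias towards the null: observed differences of 0.355 to 0.595 could gain significance. The probabilities are 21% and 7%.

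These are chances of landing in a sensitive region, not chances of a wrong verdict. In any one trial the bias has only one sign, so the two should not be added.

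**5. An observed 1-step difference.** With the shift in the ECS arm only, significance is lost when the missing ECS children sit (1 − 0.595)/0.12 = 3.4 steps above those observed (12% loss), or (1 − 0.596)/0.18 = 2.2 steps above (18% ECS loss; critical difference 0.596 with 82 and 94 children). Both gaps exceed the assumed range.

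**The case against.** Much can be said for the plan. The restriction is stated openly in the same sentence as the label, and children are kept regardless of adherence to the intervention, so intention-to-treat is respected in that sense. Dropout is allowed for in the power table. Several features may keep losses low and similar: both arms have the same five clinic and three home assessment visits, both are paid per visit, and controls are offered most of the intervention afterwards. A related home pest-management trial cited in the Background reports about 90% retention, though not by arm. Baseline-step adjustment is foreseen and would reduce bias to the extent that baseline step explains who is lost. All this stands and lowers the likely size. None of it supplies a missing-data method, and baseline step is listed for examination without being fixed in the primary model.

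One might also argue that earlier steps say little about a late effect, since "an effect may not be observed before this time because it takes several months for indoor allergen levels to fall". An arm-by-visit term answers this, because it leaves the month-6 contrast free to differ from earlier ones. Nor are multi-visit models foreign to the plan, which tests *S. aureus* "association with asthma outcomes over multiple visits using random effects models". The telephone interview is not stated to yield a treatment step.

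A reader might infer that the result will be biased, or that the true type I error is about 12%. The documents support neither. The 12% figure needs either a 3:1 loss ratio with a 2-step gap, or a 2-step gap confined to one arm, in both cases without baseline adjustment. A reader might also infer that item f removes the sickest children from the analysis. It stops further study intervention and is silent on CV4.

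**Conclusion.** The concern holds as a gap in the analysis plan. Both analysis sets require six-month data, no planned efficacy analysis covers everyone randomised, and there is no missing-data method or sensitivity analysis for treatment step. The label is the smaller part; discarding steps already assigned at CV2 and CV3 is the larger.

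The possible bias is 0 to 0.24 step in either direction under the assumed scenarios. That range depends on the chosen splits and gaps and is not a bound. It matters for observed differences of roughly 0.36 to 0.84 step, and much less for the 1-step difference the trial was designed to detect. There is no error in the power calculation. This is a cheap improvement that should be made before losses by arm are known; it is not a flaw that undermines the design.

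**What to change.** - Define the ITT set as all randomised children in their assigned arm, including any later replaced, and rename the present set available-case.
- Make the primary estimate the 6-month arm contrast from one repeated-measures model of the steps assigned at CV2, CV3 and CV4, with arm, visit, arm-by-visit and CV1 step. Use multiple imputation for children with no post-randomisation step.
- Keep the planned available-case change analysis as supportive.
- Add one delta-adjusted tipping-point analysis, varied by arm, with imputed steps kept within 0 to 6.
- Report losses and their reasons by arm.
- Reconcile Study Procedures items f and g with the Analysis Plan: state whether discontinued children are still assessed at CV4, and whether replaced children stay in the analysis. No change to the clinical removal rule is proposed.

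The cost is plan wording and modest extra analysis. No new measurement is needed, because the step is already assigned at each clinic visit. The drawback is that the main model assumes data missing at random, and children who leave before CV2 depend wholly on imputation. The tipping-point analysis examines how far that assumption can fail before the conclusion changes.

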**Only participants sensitive to mouse or cockroach will receive INT 2.												

Screening Visit

Skin testing: Allergy skin testing will be performed to 14 allergens, using the MultiTest device (Lincoln Diagnostics, Decatur, IL). The allergen extracts to be used are: dog, cat, *Dermatophagoides pteronyssinus*, *Dermatophagoides farinae*, rat epithelia, German cockroach, American cockroach, mouse epithelia, tree pollen mix, grass mix, *Alternaria*, *Aspergillus*, common ragweed, and *Cladosporium*. A positive skin test will be defined as a net wheal ≥ 2 mm. Skin test results performed by the study team within the last year may be used for inclusion criteria. We define the mean wheal diameter as the average of the largest diameter and the corresponding midpoint diameter. Participants who are not able to have skin testing done at the screening visit or who are skin test negative may have blood drawn for specific IgE test to dog, cat, rat, *Dermatophagoides farinae* along with mouse and cockroach.

FENO and Lung Function: FENO is a known marker of pulmonary inflammation and will provide a non-invasive means of assessing pulmonary inflammation in a large cohort that includes children. Measurement of exhaled nitric oxide will be obtained prior to lung function according to the American Thoracic Society Guidelines⁽²⁵⁾ using a handheld, FDA-approved analyzer (NIOX TM System, Aerocrine, Sweden). Pre- and post-bronchodilator lung function testing will be performed according to ATS guidelines.⁽²⁶⁾ After the pre-bronchodilator lung function testing is done, the participant will be given one unit dose of nebulized albuterol (2.5mg) and spirometry will be repeated approximately 15-20 minutes following administration of albuterol. Bronchodilator reversibility will be defined as a $\geq 12\%$ increase in FEV1 after short-acting bronchodilator.

Venipuncture: A venous blood sample will be obtained so that the serum can be used to measure mouse, cockroach, staphylococcal enterotoxin-specific IgE levels in the [name] laboratory using the ImmunoCAP system (ThermoFisher, Uppsala, Sweden). Participants who are not able to complete prick puncture skin testing, or have a negative skin test but strong clinical evidence, will have specific IgE test to dog, cat, *Dermatophagoides farinae*, and rat along with mouse and cockroach.

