Randomization: Participants will be randomized within 6 weeks (+/- 2 wks) of the screening clinic visit in a 1:1 ratio using a statistical software package to generate random numbers. The randomization scheme will be developed by the Data Management and Analysis Core (DMAC). Participants will be randomized in random block sizes of 4 to 8. The randomization scheme will be embedded into the recruitment/tracking database so that once a participant meets all eligibility criteria the site study coordinator can activate randomization through a secure user interface. The DMAC database programmer will have access to the computer code for the randomization scheme. Participants randomized to the ECS+Medication Group will be scheduled for an intervention prior to their next clinic visit.

ECS Intervention

Skin test data, home inspection data, and environmental history will be used to tailor an ECS to participants randomized to the ECS+Medication Group. Randomization will occur at CV1 and all of the information needed to assign ECS modules will have been collected before randomization. The 5 modules are listed below along with the qualifying criteria to receive the module and a summary of the components of each module (Table 5).

	Qualifying criteria	Components of Module
Rodent module	Positive skin test or IgE* to mouse or rat plus any evidence of infestation on home inspection OR parent report of evidence of infestation in the past month	Professional IPM Targeted cleaning IPM education Allergen-proof mattress and pillow encasements
Cockroach module	Positive skin test or IgE* to cockroach plus any evidence of infestation on home inspection OR parent report of evidence of infestation in the past month	Professional IPM Targeted cleaning IPM education Allergen-proof mattress and pillow encasements
Furry pet module	Positive skin test or IgE* to cat or dog	Education Allergen-proof mattress and pillow encasements Targeted cleaning
Dust mite module	Positive skin test or IgE* to dust mite	Education Allergen-proof mattress and pillow encasements Targeted cleaning
SHS module	Smoker in the home	Education
Air purifiers/Clean Bedding	None – everyone assigned to the ECS+medication arm will receive air purifiers and child’s bedding will be replaced with study bedding for study duration.	Deployment of 2 portable air purifiers, one in the child’s bedroom and one in the TV/living room. Child’s bedding will be replaced with study bedding for study duration.

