* ≥ 2 mm net wheal or specific IgE ≥ 0.35		

Professional IPM will be delivered by a local pest management company using protocols we have developed for other studies. For rodents, the intervention will include placement of traps, application of rodenticide in cracks and sealing of cracks and holes that can serve as an entry point for rodents. For cockroaches, the intervention will be based on previous successful protocols^(22, 24) and will include placement of Advion (indoxacarb), a low-toxicity gel bait, and sticky traps for monitoring of cockroach infestation. Indoxacarb is the active ingredient in pesticides used on pomme fruits such as apples and in products used to kill fleas on cats and dogs. It is a commercially available pesticide for cockroach control and will be applied by licensed exterminators according to the manufacturer’s instructions.

Parents/guardians will be asked to place the sticky traps 3-4 days prior to the IPM visit so that the location(s) of cockroach activity can be accurately identified. They will be given detailed instructions along with the sticky traps. The study team may assign a team member to place the traps for the family if this seems necessary. If for some reason, traps are not placed prior to the intervention visit the IPM team may place the traps and return to the house after 3-4 days for the placement of gel bait. The IPM team will count the number of cockroaches caught on the sticky traps and use a vacuum as a cockroach removal tool. The local pest management company, Innovative Pest Management, provides protocolized IPM services for a current study. As many as four IPM visits may occur for persistent or recurrent infestation. If new evidence of mouse or cockroach is seen or reported any time between HV1 and INT 3, the appropriate module will be completed in the home before CV3.

Allergen-proof mattress and pillow encasements will be installed by study staff. These encasements block particles down to 1 micron in size so are optimal for blocking allergens such as furry animal allergens that are found on smaller particles than dust mite and cockroach allergens.

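### The per-protocol rule spells out the ECS-arm criterion only as an IPM visit, so read literally it drops fully treated ECS children who have no rodent or cockroach module

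*Combined protocol and SAP*

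**What the plan says.** Section 6.c (Analysis Plan) names two analysis sets. The primary one is intent-to-treat: everyone with six-month outcome data, whatever share of the ECS they completed. The second is per-protocol: those with six-month data who "completed at least one intervention visit (one IPM visit or for the Medication Group, receipt of ECS educational materials". Nothing else in the document defines the per-protocol set.

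The parts of the protocol that bear on this rule are:

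- **Where IPM occurs.** In Table 5 (ECS Intervention), professional IPM is a component of two modules only. The rodent module requires "Positive skin test or IgE* to mouse or rat plus any evidence of infestation on home inspection", or a parent's report of infestation. The cockroach module requires sensitisation "to cockroach plus any evidence of infestation on home inspection OR parent report of evidence of infestation in the past month". The furry pet, dust mite and second-hand smoke modules contain no IPM. Neither do the air purifiers and study bedding that every ECS child receives.
- **Which visits ECS children receive.** The visit schedule shows four intervention visits, with the footnote "Only participants sensitive to mouse or cockroach will receive INT 2". Interventions 1, 3 and 4 carry no such restriction. Section 3.b counts up to four environmental intervention visits for the ECS arm.
- **Who may enrol.** Section 4 accepts sensitisation to any one of cat, dog, mouse, rat, cockroach or dust mite. Infestation is not required.
- **How the Medication Group qualifies.** Its educational materials are given at CV1, which is also the randomisation visit.

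**The concern.** The parenthesis gives one criterion per arm. For the ECS arm that criterion is an IPM visit, and nothing marks it as an example. A child sensitised only to cat, dog or dust mite, with no pest evidence in the home, is never due an IPM visit. That child can receive the purifiers, bedding, encasements, cleaning and education, attend every assigned visit, and still fall outside the set as worded.

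The larger problem is selection rather than lost numbers. Under the literal rule, ECS children are kept according to pest sensitisation and infestation, whereas Medication Group children are kept for having been handed materials at CV1. The two groups would then differ in baseline characteristics as well as in what they received. Part of the ECS selection would also happen after randomisation, because a module can be added later: "If new evidence of mouse or cockroach is seen or reported any time between HV1 and INT 3", the module is delivered before CV3. The Medication Group has no matching step during follow-up.

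If the wording stays open, the choice between two different per-protocol sets could be made after the data have been seen.

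**Working it through.** **1. The two readings applied to the same child.** Take an ECS child sensitised to cat only, with no sign or report of pests, who attends Interventions 1, 3 and 4 and has six-month data.

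- General clause (any intervention visit): three visits completed, so the child is included.
- Parenthesis as written (an IPM visit): none completed, so the child is excluded.
- The same child in the Medication Group: materials received at CV1, so the child is included on either reading.

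**2. Does usage elsewhere settle the meaning?** It does not. Section 7.a, on cleaning and caulking agents, treats intervention visits and IPM visits as separate things: cleaning happens at the first and last of the former, sealing of holes at the latter. The ECS Intervention section uses both terms for one visit. It says "Parents/guardians will be asked to place the sticky traps 3-4 days prior to the IPM visit" and shortly afterwards "If for some reason, traps are not placed prior to the intervention visit the IPM team may place the traps".

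**3. Could module status have been applied to both arms?** The ECS Intervention section says "all of the information needed to assign ECS modules will have been collected before randomization". Baseline module eligibility is therefore knowable for the Medication Group too, but the per-protocol rule does not use it there.

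**4. Size, for illustration only.** The plan gives no figure for the per-protocol set, so there is none to reproduce. The completer count and SD are borrowed from the power section. A check on those inputs, using the normal approximation with two-sided alpha 0.05 (the plan does not state sidedness), a difference of 1 step and SD 2:

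- n = 200: 1 / (2 × √(2/100)) = 3.536; 3.536 − 1.960 = 1.576; power 0.94. The plan states 0.94.
- n = 175: 1 / (2 × √(2/87.5)) = 3.307; 3.307 − 1.960 = 1.347; power 0.91. The plan states 0.90, which agrees to within about a point.

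Inputs for the per-protocol illustration:

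- Completers per arm: 175 / 2 = 87.5 (Table 6, 1:1 allocation).
- SD = 2 (Table 6). This is assumed to carry over to the per-protocol contrast.
- f = share of ECS completers with at least one IPM visit. **The documents do not give f; the values below are assumptions.**
- All ECS completers are assumed to have attended at least one intervention visit of some kind.

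Formulas: dropped = 87.5 × (1 − f); SE = 2 × √(1/87.5 + 1/(87.5f)); 95% half-width = 1.96 × SE. Relative to f = 1, the half-width is multiplied by √((1 + 1/f)/2), which does not depend on the SD.

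| f (assumed) | ECS completers dropped | SE | Half-width (steps) | Change |
|---|---|---|---|---|
| 1 | 0 | 0.302 | 0.593 | – |
| 0.9 | 8.75 | 0.311 | 0.609 | +2.7% |
| 0.7 | 26.25 | 0.333 | 0.653 | +10.2% |
| 0.5 | 43.75 | 0.370 | 0.726 | +22.5% |

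The documents hint that f may be high: parent report also counts as pest evidence, modules can be added during follow-up, and the community is described as having high airborne mouse allergen. None of this fixes a value. Under the general clause no child is dropped for lacking a pest module.

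**The case against.** The best case for leaving the text alone is that the operative test is the general clause and the parenthesis is only a loose gloss. Every ECS child is scheduled for non-pest intervention visits, and section 3.b calls all of them environmental intervention visits. A rule that labels a child who attended every assigned visit as off protocol would contradict the clause it explains. This makes the harmless reading the more natural one. It does not make it the written one: that reading works only by setting aside the sole criterion stated for the ECS arm. If an IPM requirement was in fact intended, the parenthesis says so, but the selection then acts on one arm only.

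The analysis also has safeguards. Section 6.c compares change from baseline in treatment step, which removes a stable difference in level. It names baseline allergen and pollutant levels among the confounders to be examined closely, and again as effect modifiers with stratification and interaction terms. The measured allergens include mouse and cockroach. The number of positive skin tests is a further named modifier. These steps may well shrink an imbalance. They do not guarantee its removal, because an allergen level is not the same as sensitisation plus infestation, and the text does not commit to a fixed adjustment set for the per-protocol comparison.

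The objection that the sizes rest on an assumed share also stands. The figures above are illustrations, not estimates.

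**Conclusion.** The point holds as a minor one. As worded, the per-protocol rule can exclude fully treated ECS children and select the ECS arm alone on pest status, and the general clause and the parenthesis give different sets. The effect is confined to a supplementary analysis. The intent-to-treat analysis does not use this rule, and the sample size does not rest on it.

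Three stronger conclusions might be inferred, and the documents do not support them:

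- **That the per-protocol result would be biased by a known amount or in a known direction.** Neither can be derived.
- **That pest-module status would be out of balance between the arms by 1 − f.** Modules are not assigned in the Medication Group during the trial, and f in the ECS arm mixes baseline with later qualification, so the control-arm counterpart is undefined.
- **That the per-protocol analysis would lack power.** The plan makes no power claim for it, and the loss of precision is about 3% at f = 0.9 and reaches about 10% only near f = 0.7.

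The textual conclusion needs no assumption. The illustrative figures depend on the assumed f and on 87.5 completers per arm; the absolute half-widths also depend on SD 2.

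**What to change.** In section 6.c, reword the parenthesis so that an ECS child qualifies by completing one or more assigned intervention visits (any of Interventions 1 to 4), whether or not the visit includes IPM. Keep receipt of the educational materials as the Medication Group criterion. Make the change before outcome data are examined by arm.

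The cost is one phrase in the analysis plan. It needs no new data, no change to visits or modules, and no additional subgroup analysis.
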